Grade 4	
 Immediately and permanently discontinue treatment with LY3214996 and abemaciclib. Continue ongoing rash management treatment. Provide intravenous hydration or electrolyte replacement if needed. Request dermatologist advice if needed.

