Grade 2 (Persistent or recurrent following resumption of therapy)	Hold* until ≤ Grade 1. Reduce by 1 dose level.	Hold* until ≤ Grade 1. Reduce by 1 dose level.
Grade 3	Hold* until ≤ Grade 1. Reduce by 1 dose level.	Hold* until ≤ Grade 1. Reduce by 1 dose level.
Grade 4	Hold* until ≤ Grade 1. Reduce by 1 dose level.	Hold* until ≤ Grade 1. Reduce by 1 dose level.
*Patients requiring a delay of all protocol therapy > 3 weeks due to toxicity should go off protocol therapy. ** After optimal anti-diarrheal therapy. Please refer to Section 8.6.1 . Use of prophylactic or scheduled anti-diarrheals are recommended in future cycles for patients experiencing grade 2 or higher diarrhea.		

Hepatotoxicity is a known adverse drug reaction of abemaciclib. Additional information is in the IB. Should a patient experience ≥ Grade 2 increase in AST and/or ALT we recommend holding therapy with dosing guidelines below. Please follow AST, ALT, and total bilirubin at least weekly until ≤ Grade 1 prior to re-initiating study therapy. Liver function can be monitored more frequently per investigator discretion.

AST and/or ALT Elevations**	Abemaciclib	LY3214996
≤ Grade 1 (>ULN-3.0x ULN)	No change in dose.	No change in dose.
Grade 2 (>3.0-5.0 x ULN) (without increase in total bili > 2 x ULN)	Hold* until meets treatment criteria. Resume at same dose level.	Hold* until meets treatment criteria. Resume at same dose level.
Grade 2 (without increase in total bili >2 x ULN; recurrent or persistent)	Hold* until ≤ Grade 1. Reduce by 1 dose level.	Hold* until ≤ Grade 1. Reduce by 1 dose level.
Grade 3 (>5.0-20.0 x ULN) (without increase in total bili > 2 x ULN)	Hold* until ≤ Grade 1. Reduce by 1 dose level.	Hold* until ≤ Grade 1. Reduce by 1 dose level.
Grade 2 (with increase in total bili > 2x ULN)	Discontinue therapy	Discontinue therapy
Grade 3 (with increase in total bili >2 x ULN)	Discontinue therapy	Discontinue therapy
Grade 4 (>20.0 x ULN)	Discontinue therapy	Discontinue therapy
*Patients requiring a delay of all protocol therapy > 3 weeks due to toxicity should go off protocol therapy. ** Use ULN unless baseline is greater than ULN, then use baseline for grading.		

Interstitial lung disease (ILD)/pneumonitis has been identified as an adverse drug reaction for abemaciclib. Additional information is available in the IB.

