Ask your patients to report any new or worsening respiratory symptoms such as cough, dyspnea, fever, and investigate and treat as per your local clinical practice, including corticosteroids as appropriate. If interstitial lung disease/pneumonitis is suspected, investigations may include imaging, such as high-resolution CT scans, bronchoalveolar lavage, and biopsy as clinically indicated. Please refer to dosing guidelines below for respiratory toxicity.

ILD/Pneumonitis	Abemaciclib	LY3214996
≤ Grade 1	No change in dose.	No change in dose.
Grade 2 (>7 days despite maximal supportive measures or recurrent)	Hold* until ≤ Grade 1 or baseline. Reduce by 1 dose level.	Hold* until ≤ Grade 1 or baseline. Resume at same dose level.
Grade 3/4	Discontinue therapy.	Discontinue therapy.
*Patients requiring a delay of all protocol therapy > 3 weeks due to toxicity should go off protocol therapy.		

Cutaneous toxicity should be managed per guidelines in [Section 8.6.1.1](#). In the event of grade 3 or higher dermatologic toxicity, hold abemaciclib and LY3214996 until dermatologic toxicity resolves to ≤ grade 2 or pre-treatment baseline. Subsequent LY3214996 treatment should be dose reduced by one dose level. Abemaciclib does not require dose reduction. Treatment may be held for up to 21 days. If the toxicity is not improved to ≤ grade 2 or pre-treatment baseline within the 21-day period, the patient will discontinue therapy. Additionally, a one level dose reduction of LY3214996 is permitted for intolerable grade 2 dermatologic toxicity, at the discretion of the treating physician. Such dose reductions should be undertaken in conjunction with management of cutaneous toxicity as described in [Section 8.6.1.1](#).

For any grade 3 or 4 toxicity, not mentioned above, the treatment should be withheld until the patient recovers to grade 1 or less toxicity. The treatment may then be resumed at one dose level reduction. For intolerable grade 2 toxicities, withhold treatment until the patient recovers, then resume treatment at a one dose level reduction. Dose reduction will be done for the drug that is most likely to have caused the toxicity. For grade 1 or tolerable grade 2 toxicities or clinically insignificant laboratory changes, no dose reduction should be made.

Dose adjustments as outlined in the table below are allowed both within a cycle and between cycles for abemaciclib. Abemaciclib must be reduced sequentially by 1 dose level.

Dose Adjustment	Oral Dose	Frequency

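### Appendix 4 permits rechallenge after Grade 4 skin toxicity, where Table 8.1 stops both drugs for good; Section 8.3 bars a re-escalation that Table 8.1 allows

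*Combined protocol and SAP*

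**What the plan says.** Three places govern dosing after a skin reaction.

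- **Appendix 4, cutaneous toxicity paragraph.** It opens with "Cutaneous toxicity should be managed per guidelines in" Section 8.6.1.1 and then states a rule of its own: "In the event of grade 3 or higher dermatologic toxicity, hold abemaciclib and LY3214996 until dermatologic toxicity resolves" to Grade 2 or less, or to baseline. On resumption, "Subsequent LY3214996 treatment should be dose reduced by one dose level" and "Abemaciclib does not require dose reduction". The one stopping condition is failure to improve to Grade 2 or less or "pre-treatment baseline within the 21-day period, the patient will discontinue therapy". After a sentence allowing a reduction for intolerable Grade 2 toxicity, the paragraph closes by pointing to Section 8.6.1.1 again: "Such dose reductions should be undertaken in conjunction with management of cutaneous toxicity as described in" that section.
- **Section 8.6.1.1, Table 8.1.** At Grade 3, both drugs are held for up to 21 days and LY3214996 restarts one level lower. It may return to the previous level if a further cycle passes without recurrence. At Grade 4: "Immediately and permanently discontinue treatment with LY3214996 and abemaciclib". The section describes its content as guidance that does not displace the investigator's judgment.
- **Section 8.3.** It sends the reader to Appendix 4 for dose adjustment. It also requires that a patient whose dose has been adjusted stay at the reduced level for every remaining cycle. Skin rash appears there only as an exception to the three-week recovery rule.

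**The concern.** Two instructions differ. All the texts stop both drugs at once for a Grade 4 skin reaction, but they part on what follows: Appendix 4 leaves a route back to both drugs, and Table 8.1 closes it. After Grade 3 rash, returning LY3214996 to 200 mg is permitted in one section and ruled out in another.

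The first difference matters more, because it concerns re-exposure after a Grade 4 reaction. The protocol expects rash with LY3214996 (Section 8.6.1.1) and reports more maculo-papular rash and acneiform dermatitis with the combination in dose escalation (Section 3.1.2.1.2). Two investigators could treat the same reaction differently and each cite the protocol. The difference would then carry into the safety summaries and the summaries of dose reductions and dose intensity planned in Section 14.3.2.7.

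**Working it through.** **The texts side by side**

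| Situation | Appendix 4 | Table 8.1 | Section 8.3 |
|---|---|---|---|
| Grade 4 skin reaction, improved to Grade 2 within 21 days | May resume: LY3214996 one level lower, abemaciclib unreduced | Both drugs permanently off | Refers to Appendix 4 |
| Grade 3 rash, LY3214996 reduced, one further cycle without recurrence | Silent on re-escalation | LY3214996 may return to previous level | Reduced level kept for all remaining cycles |

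**Grade 4 case.** Take a patient on full doses whose Grade 4 reaction improves to Grade 2 by day 20. Under Appendix 4 this patient can restart LY3214996 at 100 mg daily and abemaciclib at 150 mg every 12 hours. Under Table 8.1 the patient is off both. Nothing in the documents says which text prevails.

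**Re-escalation case.** LY3214996 has one reduction step, 200 mg to 100 mg (Appendix 4). Per 28-day cycle the two readings give:

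- Re-escalated as Table 8.1 allows: 28 × 200 = 5600 mg.
- Kept at the reduced level as Section 8.3 requires: 28 × 100 = 2800 mg.

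**How often the rules might be needed.** Table 3.2 pools Grade 3 and above, so a Grade 4 rate cannot be extracted. Its related skin entries of Grade 3 or higher are:

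| Term | Part A | Part A2 | Part B | Part C | Total of 108 |
|---|---|---|---|---|---|
| Maculopapular rash | 1 | 3 | 0 | 0 | 4 (3.7%) |
| Acneiform dermatitis | 0 | 0 | 2 | 0 | 2 (1.9%) |
| Rash | 0 | 1 | 0 | 0 | 1 (0.9%) |
| Pruritus | 0 | 1 | 0 | 0 | 1 (0.9%) |
| Entries | 1 | 5 | 2 | 0 | 8 |

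Parts D and JP have none. One patient can appear under several terms. Taking each patient to be in one part:

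- Fewest distinct patients: 1 + 3 + 2 = 6, and 6/108 = 5.6%.
- Most distinct patients: 1 + 5 + 2 = 8, and 8/108 = 7.4%.
- Scaled to this trial: 6/108 × 28 = 1.6 at the low end, 8/108 × 35 = 2.6 at the high end.

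Part C, the abemaciclib combination, had 0 of 20 for all four terms. The exact two-sided 95% upper limit is 1 − 0.025^(1/20) = 16.8%, so zero observed does not exclude an appreciable rate. Table 3.1 lists one Grade 3 rash DLT on the combination, at 400 mg daily plus 150 mg twice daily. None of the 6 evaluable patients at this trial's dose had a skin DLT. Table 3.1 shows 9 + 15 + 8 + 5 + 12 = 49 enrolled on the combination against 20 in Part C of Table 3.2, so the two tables do not describe the same set of patients.

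**The case against.** The strongest reply is that the Grade 4 stop is already in the section to which Appendix 4 sends the reader, at both ends of its paragraph. Appendix 4 also does not order a restart; it sets the LY3214996 level if treatment resumes. An investigator who stops permanently at Grade 4 complies with both texts. All of this stands. It narrows the fault to a missing Grade 4 exception, but does not remove it: the Appendix 4 rule expressly reaches above Grade 3, carries its own resumption terms and has a single stopping condition, which is lack of recovery.

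On re-escalation, Table 8.1 gives a permission and Section 8.3 a requirement, so never re-escalating satisfies both. That also stands. The fault is that an investigator who uses the permission breaks Section 8.3.

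Three stronger readings may tempt a reader, and the documents do not support them:

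- *Appendix 4 overrides Table 8.1 because the latter is only guidance.* Section 8.3 calls the Appendix 4 content guidelines too, and Table 8.1 also contains drug-specific dose instructions. No ranking is stated either way.
- *There is no Grade 4 stop for skin, because Appendix 4 writes one out for liver enzymes and pneumonitis but not here.* The stop is written, in the section that Appendix 4 cites.
- *The growth-factor row of the anemia table is a further conflict, because it suspends only abemaciclib.* Section 8.6.1 holds study therapy when G-CSF is required, Section 8.6.1.4 suspends both drugs, and the neutropenia note in Appendix 4 suspends therapy. The row's LY3214996 entry can be read as no change of dose level.

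**Conclusion.** The skin-toxicity dose rules are inconsistent in two places and should be corrected. Appendix 4 as written permits rechallenge with both drugs after a Grade 4 skin reaction that recovers within 21 days, against Table 8.1. Section 8.3 forbids the LY3214996 re-escalation that Table 8.1 allows after Grade 3 rash, a twofold difference in dose per cycle for an affected patient.

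The number affected is probably small but poorly known. No frequency can be given for Grade 4. The 1.6 to 2.6 patients with a skin event of Grade 3 or higher assume that the pooled phase 1 rates carry over, although 5 of the 8 entries came from Part A2, the twice-daily part, and none from the combination in Table 3.2. That figure is neither a Grade 4 estimate nor a bound.

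The consequence is for patient safety and consistency of dosing. The primary ORR test, its threshold of 4 responders in 28, the sample size and the power do not depend on it.

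**What to change.** 1. In Appendix 4, limit the hold-and-resume rule for dermatologic toxicity to Grade 3, and add: *Grade 4: permanently discontinue LY3214996 and abemaciclib, per Table 8.1.*
2. Decide whether re-escalation is wanted. If it is, add to the Section 8.3 rule on reduced doses: *except LY3214996 after Grade 3 rash, as allowed in Table 8.1.* If it is not, delete the re-escalation bullet from the Grade 3 row of Table 8.1.

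The cost is amendment wording only. No assessment, sample size or analysis changes.

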Appendix 5. Sensitive CYP3A Substrates and Narrow Therapeutic Range Drugs

The information in this table is provided for guidance to investigators and does not preclude the use of these medications if clinically indicated.

Strong Inducers of CYP3A

Carbamazepine
Dexamethasone
Phenobarbital/phenobarbitone
Phenytoin
Rifapentine
Rifampin
Rifabutin
St John's wort

Moderate Inducers of CYP3A

Bosentan
Lenisurad
Modafinil
Primidone
Telotristat ethyl

Strong Inhibitors of CYP3A

Aprepitant
Ciprofloxacin
Clarithromycin
Conivaptan
Diltiazem
Erythromycin
Fluconazole
Itraconazole
Ketoconazole
Nefazodone
Posaconazole
Troleandomycin
Verapamil

This table is prepared to provide examples of clinical CYP3A-sensitive substrates and narrow therapeutic range drugs that are CYP3A substrates and is not intended to be an exhaustive list. Concomitant therapy with sensitive substrates of CYP3A4, particularly those that also have a narrow therapeutic range, should be used with caution for all patients.

Appendix 6. Patient Dosing Instructions and Diary

Subject ID: _____ Cycle: _____

Date Medication Dispensed ____/____/____

LY3214996 _____

Abemaciclib Dose: _____

Dosing Instructions

LY3214996

- You will take LY3214996 once daily on days 1 through 28 of your 28 day cycle
- LY3214996 can be taken with or without food
- You should take your dose about the same time each day (\pm 2 hours) as much as possible
- If you miss or vomit a dose, you should not take another dose to try and make it up
- LY3214996 should be taken at the same time as either the a.m. or p.m. dose of abemaciclib

Abemaciclib

- You will take abemaciclib twice a day on days 1 through 28 of your 28 day cycle
- You should take your doses 12 hours apart (\pm 2 hours) and at about the same time each day
- Abemaciclib can be taken with or without food
- If you miss or vomit a dose, you should not take another dose to try and make it up

Dosing Diary

Subject ID: _____ Cycle: _____

Use the table below to record each dose of LY3214996 and each dose of Abemaciclib you take. Record the date and the time of each dose in the space provided. Return your diary to the study team at the end of each cycle.

Day	LY3214996	Abemaciclib	Day	LY3214996	Abemaciclib
Example Day 1 01/01/2001	8:00 am	8:00 am 8:00 pm			
Day 1: ___/___/___	___:___	___:___ ___:___	Day 15: ___/___/___	___:___	___:___ ___:___
Day 2: ___/___/___	___:___	___:___ ___:___	Day 16: ___/___/___	___:___	___:___ ___:___
Day 3: ___/___/___	___:___	___:___ ___:___	Day 17: ___/___/___	___:___	___:___ ___:___
Day 4: ___/___/___	___:___	___:___ ___:___	Day 18: ___/___/___	___:___	___:___ ___:___
Day 5: ___/___/___	___:___	___:___ ___:___	Day 19: ___/___/___	___:___	___:___ ___:___
Day 6: ___/___/___	___:___	___:___ ___:___	Day 20: ___/___/___	___:___	___:___ ___:___
Day 7: ___/___/___	___:___	___:___ ___:___	Day 21: ___/___/___	___:___	___:___ ___:___
Day 8: ___/___/___	___:___	___:___ ___:___	Day 22: ___/___/___	___:___	___:___ ___:___
Day 9: ___/___/___	___:___	___:___ ___:___	Day 23: ___/___/___	___:___	___:___ ___:___
Day 10: ___/___/___	___:___	___:___ ___:___	Day 24: ___/___/___	___:___	___:___ ___:___
Day 11: ___/___/___	___:___	___:___ ___:___	Day 25: ___/___/___	___:___	___:___ ___:___
Day 12: ___/___/___	___:___	___:___ ___:___	Day 26: ___/___/___	___:___	___:___ ___:___
Day 13: ___/___/___	___:___	___:___ ___:___	Day 27: ___/___/___	___:___	___:___ ___:___
Day 14: ___/___/___	___:___	___:___ ___:___	Day 28: ___/___/___	___:___	___:___ ___:___
